## **9.2 Setting**

This study will be conducted in Spain where the 1st COVID-19 vaccine was included in public campaigns after approval by the European Commission from 21st December 2020. The eligibility criteria will change over time according to prioritised vaccination groups as follows in Figure 1:

Due to the potentially changing incidence of COVID-19 over time and prioritised vaccination groups, comparisons within the study periods and prioritised criteria will be established as much as possible.

According to the 1st prioritized groups (see Figure above), the **study period** will begin on the 21st of December 2020. The end of study period will be the last date of data received at the start of the data collection. Since the vaccines start to request the vaccination for young people (for example: Pfizer requested to the FDA to expand use of its Covid-19 vaccine to adolescents ages 12 to 15 on 9th April 2021), no age restriction will be applied for the source population.

No sex restriction will be applied.

In BIFAP, as per quality and quantity criteria for research, and in order to ensure precise anamnesis, only those clinical histories considered up-to-standard are included in pharmacoepidemiological studies.

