### 9.3.1 Exposure Assessment and Time At Risk

Data will be collected from BIFAP database with data from Spain (described in [Data Sources](#)).

**Inclusion criteria** to the Source population: up-to-standard,  $\geq 1$  year baseline information in January 2021 in BIFAP. The last date of filling all the inclusion criteria will be the inclusion date. No restriction to age or sex will be applied.

**Exclusion criteria:** Patients with prevalent COVID vaccinations or infections ever before (i.e. washout period) the inclusion criteria will be excluded.

**Stop date:** the last moment of the following criteria will define the stop date to contribution: covid-19 infection, death, loss to follow-up and end of study period (the last date available in the data source at data collection).

**Exposure assessment:** The 1st vaccination recorded after the inclusion date will be the time zero for patients included in the vaccinated group, as explained in section 'Definition of Time Zero' [9.1.1.4](#).

From the source population, 10 individuals unvaccinated on or before time zero of the vaccinated pair (10:1) will be randomly selected among those with similar birth cohort, sex and region (matched criteria). Patients included in the comparison group, may be vaccinated later during their follow-up period and then contribute to the vaccinated group (from the date of vaccine administration ahead; i.e. time zero for the vaccinated group).

\*Note: All individuals vaccinated during their follow-up contribution will be included in the vaccinated group. While, a random selection of the unvaccinated individuals will be included as unvaccinated group.

The date and type of vaccine administered will be collected from the **Table of Vaccine** from BIFAP data model. In particular, Covid-19 vaccinations will be ascertained from official covid-19 vaccination registries and provided by the regional governments. The coding system is not known yet. The feasibility analysis will include an evaluation of the coding type, whether or not vaccines are recorded according to standardised system or not. We expect that either ATC07 (J07????) or National Code (CNF [Código Nacional de

Farmacia]) specific for pharmaceuticals in Spain is available for all vaccines administered.

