For the vaccines currently available, those with a 2-dose regimen, the second dose must be administered 21/28 days after the 1st dose. In order to identify potential data **entry errors** (e.g., two vaccination records too closed or 3 doses recorded, may indicate double recording of the same vaccination) and cut-off points, a description of interval between doses will be performed beforehand.

Current vaccines are intended to give protection at least for 21 and 28 days after the 2nd dose, however the protection in the median-long run is unknown. Thus, in order to estimate the duration of the effectiveness, the follow-up period after 2nd dose will be divided as aforementioned.

The **follow-up** period will be the time between time zero and stop date.

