#### **9.3.3.2 Symptomatic or Asymptomatic Diagnosis of COVID-19**

In a secondary analysis, in order to inform about the effectiveness to protect against asymptomatic and symptomatic infections, outcomes from the main analysis will be divided according to the symptoms recorded around the date of confirmed covid-19 in the patient PC eHR. Two effectiveness parameter, i.e. to protect against asymptomatic and asymptomatic infection, will be estimated separately for each vaccine. The date of the COVID cases will be the 1st date the sample was taken for testing.

Cases of **Asymptomatic** infection will be defined as a positive test without recorded symptoms in primary care  $\pm$ 14days, hospitalisations/Intensive care unit (ICU) or hospital diagnosis of the date the sample was taken). In asymptomatic analysis, symptomatic infections will participate as non-cases stopping at covid date.

Cases of **Symptomatic** infection will be defined as a positive test with recorded symptoms in primary care  $\pm$ 14days of the date the sample was taken, or linked Hospitalisations/Intensive care unit (ICU) admissions. In symptomatic analysis, asymptomatic infections will participate as non-cases stopping at covid date.

Note: In epidemiological vigilance protocols, among asymptomatic patients, isolation must be maintained till 10 days after the date when the sample was taken. For a sensitive approach we will broaden till 14 days in order to allow for delayed records in PC eHR.

\*Note: some misclassification may be present since patients with mild disease (mild symptoms) may never seek care that will be assumed as asymptomatic.

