### **9.7.2 Incidence Analysis**

The crude incidence rates of the COVID-19 outcomes will be estimated after time zero for the vaccinated and unvaccinated groups for each brand.

Additionally, each vaccination strategy (e.g., fully completed on time, partially completed, delayed completion; see Section 9.3.1 and **iError! No se encuentra el origen de la referencia.**), for the same brand will be considered a separate exposure group and compared to unvaccinated.

Crude incidence rates (with 95% CI) will be estimated using the number of outcome events as the numerator and the number of person-years of follow-up as the denominator for the study periods defined.

Additionally, cumulative incidence curves (1 minus the Kaplan–Meier risk) for outcomes will be estimated to visualise the occurrence of COVID-19 outcomes over time since time zero [38].

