### **9.7.3 Comparative Analysis**

#### **9.7.3.1 Estimation of Vaccine Effectiveness**

Cox proportional hazards regression, yielding a hazard ratio (HR; 95%CI), accounting for censoring, changing incidence over time, and competing risks (Section 9.7.3.3) will be estimated for the defined periods: i.e. 0 to 14 days after D1, 15 after D1 until D2, 0 to 14 days after D2 and 15-90 days, 91-180 days, and  $\geq 181$  days after D2 in comparison with similar followed periods from time zero in the unvaccinated group.

This method will calculate a single vaccine effectiveness measure for each period of observation (assumed constant over those defined periods) in vaccinated versus unvaccinated groups. Crude vaccine effectiveness will be calculated for all the outcomes as 1 minus HR.

The assumption of proportionality of the survival curves in the vaccinated and unvaccinated groups will be evaluated.

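### The stop date in Section 9.3.1 is the last of infection, death, loss and end of study, so as printed it is always end of study and contradicts Sections 9.3.3.2 and 9.3.3.3

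*Protocol*

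**What the plan says.** Section 9.3.1 gives the only general rule for the end of follow-up: "the last moment of the following criteria will define the stop date to contribution: covid-19 infection, death, loss to follow-up", and then "end of study period (the last date available in the data source at data collection". Section 9.2 defines end of study in the same way: "The end of study period will be the last date of data received at the start of the data collection".

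Section 9.3.1 then makes follow-up depend on this date: the "period will be the time between time zero and stop date". Section 9.7.2 uses "the number of person-years of follow-up as the denominator" of the incidence rates. Section 9.7.3.1 fits a Cox model "accounting for censoring, changing incidence over time, and competing risks", with separate hazard ratios for periods counted from each dose. The ENCePP checklist (item 4.2.5) also points to the stop date as what fixes the duration of follow-up.

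The secondary outcomes follow a different rule. Section 9.3.3.2 says: "In symptomatic analysis, asymptomatic infections will participate as non-cases stopping at covid date". It says the same of symptomatic infections in the asymptomatic analysis, and Section 9.3.3.3 does so for non-severe infections in the hospitalisation analysis, where cases are dated at admission. Sections 9.3.3.4 and 9.3.3.5 count deaths up to 8 weeks after COVID-19.

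**The concern.** A time at risk should end when a person has had the event, can no longer have it, or can no longer be observed. That is the earliest of the listed dates. The printed rule takes the latest.

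Every crude rate and every hazard ratio rests on this definition. Followed literally, it keeps people in the denominator who are already infected, dead or gone. It also gives the Cox model an exit time that carries no information about when anything happened. The primary outcome, laboratory-confirmed infection (Section 9.3.3.1), has no stopping rule of its own to override it.

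**Working it through.** **1. What the rule resolves to.** Let I, D, L and E be the dates of infection, death, loss to follow-up and end of study. The printed rule is stop = max(I, D, L, E). E applies to everyone and is the last date in the data, so I, D and L cannot exceed E and the result is always E. The protocol fixes no calendar date for E. For illustration, take 30 June 2021 (data collection starts at the end of June 2021 in Section 6). Counted from 21 December 2020, that is 191 days, the longest possible follow-up under this assumption.

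| History (day) | Latest, as printed | Earliest |
|---|---|---|
| Infection 40 | 191 | 40 |
| Death 60 | 191 | 60 |
| Loss 90 | 191 | 90 |
| Infection 40, death 55 | 191 | 40 |
| None | 191 | 191 |

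**2. Conflict between sections.** In the symptomatic analysis, a person with an asymptomatic infection on day 40 stops on day 40 under Section 9.3.3.2 and on day 191 under Section 9.3.1. Both cannot hold.

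**3. Effect in the Cox model.** Suppose the first dose is on day 0, the second on day 21 (one of the two intervals named in Section 9.3.1) and infection on day 40. The infection falls 40 − 21 = 19 days after the second dose, in the 15–90 day period. If the stop date is used as the exit time, the event falls 191 − 21 = 170 days after the second dose, in the 91–180 day period. Event timing and allocation to dose periods are lost. A programmer who kept the sample date for events would avoid this, but dead and lost people would still stay in the risk sets.

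**4. Size from retaining infected people.** No figure in the plan depends on this rule; Tables 1 and 2 use cumulative risks. Assume a constant hazard λ over T = 191 days.

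- Inflation of unvaccinated person-time = λT / (1 − exp(−λT)) − 1.
- Rate-based effectiveness under the printed rule = 1 − [1 − exp(−RR·λT)] / [1 − exp(−λT)]. Under the earliest-date rule it is 1 − RR.

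At the Section 9.5 incidence of 60.57 per 100,000 in 14 days, λT = −ln(1 − 0.0006057) × 191/14 = 0.00827 and cumulative infection is 0.82%. The other two rows assume that the lowest and highest Table 2 risks apply to the 191 days.

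| Unvaccinated risk | Person-time inflation | VE 95.0% becomes | VE 66.9% becomes |
|---|---|---|---|
| 0.82% | 0.41% | 94.98% | 66.8% |
| 5.31% | 2.75% | 94.9% | 66.3% |
| 7.23% | 3.80% | 94.8% | 66.1% |

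**5. Size from retaining dead or lost people.** The protocol gives no death or deregistration rate. With an assumed non-COVID mortality of 10% per year, equal in both groups, inflation in the three rows becomes 3.1%, 5.4% and 6.5%, and VE is essentially as in the table. More generally, at an exit rate q per year over 0.5 year, the share of spurious person-time is 1 − [(1 − exp(−0.5q))/q]/0.5. That is 0.5% at q = 2% and 4.8% at q = 20%. If the groups sat at opposite ends of that assumed range, the rate ratio would change by 0.9950/0.9516 = 1.046 or its inverse, and a VE of 66.9% would become 1 − 0.331 × 1.046 = 65.4%, or 1 − 0.331/1.046 = 68.4%.

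**The case against.** The strongest reply is that this is a slip of wording and not a choice of analysis. Other sections presuppose stopping at the event: infected non-cases stop at the COVID date, the main outcome is incident infection dated at the first sample, the Cox model accounts for censoring, and Section 9.7.3.3 treats non-COVID death as a competing event. A programmer would probably notice. This stands as to intent. It does not remove the need for correction, because the sentence is the operative definition and the primary outcome has no other.

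A reader might also infer three stronger points that the document does not support.

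- *Vaccine effectiveness would be badly biased.* At the stated incidence the shift is about 0.1 percentage point or less. Larger shifts need exit rates that differ sharply between groups, and the protocol gives no such rates.
- *The list wrongly omits vaccination.* The rule governs the end of contribution, and vaccination does not end it. Section 9.3.1 moves a vaccinated comparator to the vaccinated group from the vaccination date, and Section 9.1.1.4 limits the reference period to unexposed time.
- *Infected comparators would enter the vaccinated group as susceptible.* Section 9.1.1.4 requires all eligibility criteria to be met at time zero, which for someone crossing over is the vaccination date. Some ambiguity remains, because Section 9.3.1 words the exclusion of earlier infection relative to inclusion.

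**Conclusion.** The point holds as an error in an operative definition and as an internal contradiction. That the printed rule gives end of study for every person follows from the wording alone and needs no assumption. It conflicts with Sections 9.3.3.2 and 9.3.3.3 and is probably a drafting error for the earliest date.

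The bias from retained infected person-time is small: 66.9% to 66.8% at the Section 9.5 incidence, and to 66.1–66.3% if the Table 2 risks applied. These figures assume a constant hazard and 191 days of follow-up. The case for correction does not rest on them. It rests on the rule being unusable as a Cox exit time and incompatible with the dose periods of Section 9.7.3.1.

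**What to change.** In Section 9.3.1, replace the latest date with the earliest and state the rule by outcome:

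- **Laboratory-confirmed, symptomatic and asymptomatic infection:** the earliest of first COVID-19 infection of any type, death, loss to follow-up and end of study.
- **Hospitalisation:** non-severe infections stop at the COVID date and cases at admission, as Section 9.3.3.3 already has it; otherwise the earliest of death, loss and end of study.
- **Mortality outcomes:** the earliest of death, loss and end of study. Infection does not end follow-up, so that the deaths up to 8 weeks after COVID-19 in Sections 9.3.3.4 and 9.3.3.5 are counted.

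A single rule that stops everyone at infection would remove those deaths. A rule that stops only at the outcome under analysis would let non-case infections run past the COVID date, against Sections 9.3.3.2 and 9.3.3.3. Hence the split by outcome.

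For clarity only, add that a comparator's unvaccinated person-time ends at first vaccination, as Section 9.3.1 already implies.

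The cost is a short paragraph in the protocol and matching derivations in the programming specification. No further data are needed.

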## **8 Research Question and Objectives**

This study addresses the research question of whether vaccinations with new licenced COVID-19 vaccines, (Comirnaty, Moderna, AstraZeneca's and Janssen and subsequently

approved vaccines in the EU during the data collection), are effective in reducing the burden of COVID-19 in Spain in comparison with no vaccination periods.

**Primary objective** is to evaluate the effectiveness of each COVID-19 vaccine in reducing the covid-19 infections (confirmed through test and regardless the prognosis and clinical phenotype (i.e. whether symptomatic or asymptomatic, mild or severe).

**Secondary objectives** of this study will be splitting the effectiveness

- by the following outcomes:
  - asymptomatic (defined as a positive test (whether PCR or antigens) without recorded symptoms in primary care +/-14days of the date the sample was taken). Note: In epidemiological vigilance protocols, among asymptomatic patients, isolation must be maintained till 10 days after the date when the sample was taken.
  - symptomatic (defined as positive test (whether PCR or antigens) with recorded symptoms in primary care or Hospitalisations/Intensive care unit (ICU) admissions +/-14days of the date the sample was taken (or at anytime linked with the test result))
  - Hospitalisations/Intensive care unit (ICU) admissions for COVID-19 at anytime linked with the test result or within +/-14days of the date the sample was taken (if hospitalisation was recorded in primary care clinical profile)
  - All-cause mortality as a recorded death with COVID 19 listed as an underlying cause of death on cause-of-death registers, or a death during a hospitalisation, with COVID-19 as a listed diagnosis, or a death within a specified time period (e.g., 28 days) after a diagnosis or hospitalisation for COVID 19.
- over clinically meaningful subgroups (old people; patients with cardiovascular disease, diabetes, or chronic pulmonary disease, chronic renal impairment, treated cancer, patients with a history of transplantation, Down Syndrome found linked with the prognostic of the covid-19 infection; as well as smoking, males and obesity suspected linked with the prognosis in some studies)
- along the time since complete vaccination (up-to 3 months, 6 months and ever after).

A feasibility evaluation will be conducted before the start of the study to evaluate the availability of key data elements and the appropriateness of the study design.

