#### **9.1.1.5 Assess Potential for Unmeasured Confounding**

Unmeasured confounding is a serious threat to the estimation of vaccine effectiveness using observational data [3-9]. There may be situations where the initial recommendations for vaccination, the vaccine distribution strategy, and the uptake of the vaccine may heavily influence the magnitude and direction of confounding. Since unmeasured and unknown confusion may be present we will perform the following strategies in order to minimise then:

- unvaccinated comparator will be matched by time zero of the vaccinated pair, birth year cohort (year; it will be broad till 2-years if not enough patients to select), sex, region of the primary care practice. If available information, patients living at nursing home will be matched). Several other confounder will be controlled for through adjustment in the Cox model.
- Since multiple COVID-19 vaccines are available, recipients of different COVID-19 vaccines will be also compared with the same unvaccinated comparator and among them in a head-to-head fashion. This choice would greatly diminish, if not eliminate, confounding by indication.

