## 9.5 Study Size

All patients meeting the eligibility criteria in BIFAP will be included as source population. BIFAP includes information of around 7.7 million patients aged  $\geq 18$  years (as last updated version in 2018), which distribution by sex and age is as follows:

	TOTAL	18 - 19	20 - 24	25 - 29	30 - 34	35 - 39	40 - 44	45-49	50 - 54	55-59	60-64	65-69	70-74	75-79	80-84	85-89	90-110
TOTAL	7720843	252143	424740	465933	526002	647688	747020	717918	702323	658868	569616	493770	454787	350359	317844	246643	145189
Women	3991612	122805	209807	232836	265565	324008	369475	357547	352106	330858	290309	255848	242742	194252	187908	154500	101046
Men	3729231	129338	214933	233097	260437	323680	377545	360371	350217	328010	279307	237922	212045	156107	129936	92143	44143

Taking into account the estimated COVID vaccine effectiveness reported in clinical trials [75-78], varying assumptions of vaccine unexposed to exposed ratio, anticipated global sample sizes of patients aged  $\geq 18$  years in BIFAP, a cumulative positive symptomatic COVID cases of 60,57 per 100,000 people in 14-days in Spain (as reported on 22 March 2021 [when started the vaccination for general people, i.e. apart from health workers and nursing home residents] in [www.cnecovid.isciii.es/covid19/](http://www.cnecovid.isciii.es/covid19/)), [33], the different probabilities that the upper limit of the 95% CI of the risk ratio (RR) being below 1.00 (a correlate of the lower bound of the vaccine effectiveness estimate being above 0.00 [Section 9.7.3.1] demonstrating a protective effect of vaccination) was estimated and displayed in Table 1:

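### The windows after dose 2 hold different vaccinees, so differences between them may reflect who was vaccinated first, in either direction, and not how long protection lasts

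*Protocol*

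**What the plan says.** Section 8 of the protocol lists a secondary objective that splits effectiveness "along the time since complete vaccination (up-to 3 months, 6 months and ever after"). Section 9.3.1 states how this will be read: "in order to estimate the duration of the effectiveness, the follow-up period after" the second dose will be divided. Section 9.7.3.1 names the periods, "0 to 14 days after D2 and 15-90 days, 91-180 days, and" at least 181 days after dose 2, each taken "in comparison with similar followed periods from time zero in the unvaccinated group". It adds: "This method will calculate a single vaccine effectiveness measure for each period of observation (assumed constant over those defined periods").

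On who enters when, Section 9.2 says: "The eligibility criteria will change over time according to prioritised vaccination groups". Section 9.5 dates general vaccination to 22 March 2021, "when started the vaccination for general people, i.e. apart from health workers and nursing home residents". Section 9.1.1.5 provides that the "unvaccinated comparator will be matched by time zero of the vaccinated pair, birth year cohort", sex and region.

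Section 9.7.4.1 stratifies the primary analyses by age 80 and over, comorbidity, region and calendar month, the last because of prioritisation. It does not link these strata to the three windows. Nothing restricts a window to people who also contribute to another.

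**The concern.** Each window HR is computed on whoever is in that window. At any data cut, everyone far enough past dose 2 has contributed to days 15-90, but only those vaccinated earlier reach days 91-180 or 181 onwards. Under a roll-out by priority group, earlier also means different in age, health and exposure.

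Setting the three VEs side by side to judge duration therefore mixes two things: time since vaccination and vaccination cohort. The protocol fixes no analysis that separates them. At stake is the secondary objective on duration. A step between windows could be reported as a change in protection when it is partly or wholly a change in the people observed. Splitting by brand does not settle this, because age and priority group can still shift across windows within a brand.

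**Working it through.** **Inputs.** Windows from Section 9.7.3.1. Dose interval of 21 or 28 days, as stated in Section 9.3.1. Study start 21 December 2020, with the end at the last data received when collection starts (Section 9.2). Start of collection at the end of June 2021 (Section 6). Efficacy by age from Table 2 (Section 9.5).

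**1. The plan's own figures.** The efficacies agree with the trial counts listed under Table 2, using 1 − (risk in vaccinated / risk in comparison group):
- Moderna, 65 and over: 1 − (4/3583)/(29/3552) = 86.3% (stated 86.4%). Younger: 1 − (7/10551)/(156/10521) = 95.5% (stated 95.6%).
- Pfizer/BioNTech: 95.6% and 93.7%, as stated.
- Janssen: 63.4% and 76.1% (stated 63.7% and 76.3%).

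The probabilities of 1 in Tables 1 and 2 also reproduce. They concern each vaccine against no effect and say nothing about comparisons between windows.

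**2. Who can be in each window at a 30 June 2021 cut.** Latest first dose = cut − (first day of window + dose interval).

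| Window after dose 2 | 21-day interval | 28-day interval |
|---|---|---|
| 15-90 days | −36 d: 25 May 2021 | −43 d: 18 May 2021 |
| 91-180 days | −112 d: 10 March 2021 | −119 d: 3 March 2021 |
| 181 days or more | −202 d: 10 December 2020 | −209 d: 3 December 2020 |

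The last row lies before the study starts, so that window is empty. The middle row lies before 22 March, so that window holds nobody from the general roll-out.

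**3. Equal VE in all groups.** Let p be the younger group's share of reference events in a window. Then HR(window) = p × HR(younger) + (1 − p) × HR(older). If both HRs equal 0.05, the result is 0.05 for every p and VE is 95% in each window. Different people alone create no trend.

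**4. VE that differs by age but is constant in time.** Assumption: p = 0.5 or 0.7 in days 15-90 and p = 0 in the later window. The documents give no event shares.

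| Brand | HR younger / older | First-window VE, p = 0.5 | First-window VE, p = 0.7 | Later VE | Later/earlier HR ratio |
|---|---|---|---|---|---|
| Moderna | 0.044 / 0.136 | 1 − 0.0900 = 91.0% | 1 − 0.0716 = 92.8% | 86.4% | 1.51 to 1.90 |
| Pfizer/BioNTech | 0.044 / 0.063 | 1 − 0.0535 = 94.7% | 1 − 0.0497 = 95.0% | 93.7% | 1.18 to 1.27 |
| Janssen | 0.363 / 0.237 | 1 − 0.3000 = 70.0% | 1 − 0.3252 = 67.5% | 76.3% | 0.79 to 0.73 |

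The false changes are −4.6 to −6.4 points (Moderna), −1.0 to −1.3 (Pfizer/BioNTech) and +6.3 to +8.8 (Janssen). The Janssen row assumes that windows worded after dose 2 are applied after its single dose.

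**5. Less extreme mixing and later cuts.** Window VE = 1 − Σ(person-time × incidence × (1 − VE)) / Σ(person-time × incidence), with Table 2 group sizes. Assumptions: dose 2 spread over March-April 2021 in the older group and June-August 2021 in the younger; equal incidence in both. VE at 15-90 / 91-180 / 181 or more days:

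| Brand | Cut 31 October 2021 | Cut 31 March 2022 |
|---|---|---|
| Moderna | 93.1 / 90.1 / 86.4 | 93.2 / 93.2 / 91.4 |
| Pfizer/BioNTech | 94.8 / 94.2 / 93.7 | 94.8 / 94.8 / 94.4 |
| Janssen | 68.1 / 72.3 / 76.3 | 67.9 / 67.9 / 70.6 |

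With the older group's incidence at half to twice the younger's, the first Moderna figure at the October cut ranges from 94.1 to 91.7. With one VE of 95% in both groups, every entry is 95.0.

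**6. Residual confounding.** If early vaccinees have c times the risk of their matched comparators for reasons other than vaccination, observed VE = 1 − c × (1 − true VE). With true VE 95%, c = 2 gives 90% and c = 0.5 gives 97.5%. This too can go either way.

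**The case against.** A reader might infer that a staggered roll-out will look like waning even when protection is constant. The documents do not support that. Each window has its own unvaccinated comparator over the same follow-up, matched on calendar time zero, birth year, sex and region, and covariates are updated and adjusted for. As step 3 shows, an artefact also needs VE or residual confounding to differ by roll-out order. Its sign depends on that difference, and the Janssen figures in Table 2 point to a rise.

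Other points have weight:
- The age intervals for Moderna overlap (90.6-97.9 and 61.4-95.2), so the difference behind the larger falls is itself uncertain. A later window with no younger-group events is an extreme case.
- Section 9.1.1.3 says that the first priority groups will not be studied. At an end-of-June cut, the 91-180-day window would then be thin. However, Sections 9.7.4.1 and 9.9 say that job and residence are not available, so full exclusion is doubtful.
- The age and calendar-month strata give some help. They are stated for the primary analyses, though, and in one calendar month of follow-up people in different windows come from different vaccination cohorts.
- The protocol specifies no formal test of one window against another, and a same-persons contrast could be placed in an analysis plan that is not shown. Each window's VE remains valid for the people in it. But Section 9.3.1 itself says that the windows serve to estimate duration, and that reading requires comparing them.

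**Conclusion.** The point holds in a form that is neutral as to direction. As written, differences between the window VEs cannot be attributed to duration of protection, because time since vaccination is mixed with vaccination cohort. They may resemble waning or rising protection when neither is present.

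On Table 2 efficacies with the assumed event shares, the false change is about 5 to 6 VE points downward for Moderna, about 1 point downward for Pfizer/BioNTech, and upward for Janssen if the windows apply to it. Under the assumed roll-out dates and a March 2022 cut, the change from the first to the last window shrinks to −1.8, −0.4 and +2.7 points. It is zero if VE and residual confounding are the same across the roll-out. Selective loss of comparators who are later vaccinated was not modelled and could add bias either way.

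The point concerns the reading of a secondary objective. It does not show that any single window's estimate against the unvaccinated is wrong.

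**What to change.** In Sections 9.3.1 and 9.7.3.1:
- Base any statement on duration, by brand, on vaccinees and their matched comparators whose dose-2 date allows them to contribute to both windows compared. Select on the date, not on having remained event-free. A date early enough to cover the whole later window keeps the mix of people closest. Alternatively, estimate the window HRs within vaccination-period and age strata; this suits the open-ended last window better.
- Report the later-to-earlier HR ratio with its interval.
- Keep the all-comer window HRs as descriptive, and state that differences between them are not to be read as waning or rising protection.
- Say whether and how the windows apply to a one-dose vaccine.

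Reconcile the data cut. Sections 6 and 9.2 imply data to about the end of June 2021, while Section 9.1 speaks of deliveries every two months from 21 December 2021. On the former, the last window is empty and the restricted contrast would rest only on people with a first dose before general vaccination began.

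The cost is one restricted or stratified run of the planned model and a few sentences. The intervals will be wider, and a restricted result applies to early vaccinees only.
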